## **APPROACH**

### **Design Overview and Considerations**

We are targeting a high-risk (low SES adolescents) population at a highly relevant period (high school) for smoking onset. The study design calls for block randomization of 150 non-smoking adolescents to one of three intervention conditions: (1) a control condition offering health education combined with a smoking prevention informational intervention (C+SPII), (2) a WM intervention delivered prior to a smoking prevention informational intervention (WM+SPII), (3) a DT training intervention delivered prior to a smoking prevention informational intervention (DI+SPII). Smoking risk proximal outcomes are assessed by smoking propensity self-report, delay discounting, and implicit associations to smoking; Smoking behavior is assessed at one-month follow-up.

- **Why Utilize a SPII as a component common to all randomized conditions?** Meta-analytic review indicates that smoking prevention informational interventions can offer benefits, but there is also evidence these benefits are limited for low-SES participants. Our interventions are designed to enhance the ability of individuals to utilize standard SPIIs (by enhancing cognitive and affective self-control skills), and hence, are designed to rescue prevention outcomes for these at-risk individuals.
- **Why block randomize by parental smoking?** Parental smoking is associated with smoking attitudes among children and confers a significantly higher risk of smoking initiation. Crucially, research indicates that parental smoking is one significant mechanism by which low SES translates into youth smoking. Ensuring balance of parental smoking status across the intervention conditions allows evaluation of potential

moderating effects of this factor on interventions and outcomes.

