**Delay Discounting.** Identical to methods employed by Reynolds & Fields for adolescents experimenting with smoking, we will assess delay discounting by presenting participants with computer-based choices between \$10 available after a specified delay (i.e. 1, 2, 30, 180 or 365 days) and a smaller amount available immediately (e.g. 'would you rather have \$10 in 30 days or \$2 now?'). This computerized task uses an adjusting amount procedure (adjusting the immediate amount in increments of  $\pm \$0.50$ ) to derive indifference points. At the end of the session one question would be selected and honored—resulting in either immediate or delayed money.

**Smoking Status.** Self-reports of smoking status will be collected using time line follow-back methodology to determine the time frame of smoking initiation if it occurred. Self-reports of abstinence at each assessment visit will be verified by expired carbon monoxide (4 ppm cutoff).

**WM Capacity.** WM assessment includes these three tasks plus a warm-up task, the sequence recall of digits—auditory (SRD-A). The Sequenced Recall Reversed Digits—Auditory (SRRD-A) program is identical to the SRD-A, except that participants are required to recall the digits in the reverse order of presentation. The Sequenced Recall of Words—Visual (SRW-V) task presents a list of four-letter words on a computer screen. The Verbal Memory—Categorizing (VM-C) presents participants with 20 words falling into four categories (e.g., colors, vegetables). The WM capacity data submitted for analysis will be the z-score (using BL means and SDs) average of the SRRD-A, SRW-V, and VM-C as specified below.

**Positive and Negative Affect Schedule (PANAS).** The

negative affective score will be used as additional exploratory predictor of smoking status alone and in interaction with DT.

**Distress Tolerance.** Because self-report and behavioral measures of DT are only partially correlated, we will use both assessment strategies in the current study, with the variable submitted for analysis

Measures	Baseline	Intervention	1-Week Post-Intervention	1-Month Post Intervention
Initial Assessment				
Demographics	X			
Additional Covariates				
Parental Smoking	X			
Peer Smoking	X			
Sensation Seeking	X			
Mediator Variables				
Working Memory (WM)	X		X	
Distress Tolerance (DT)	X		X	
Proximal Smoking Risk Outcomes				
Smoking Susceptibility	X		X	X
Smoking IAT	X		X	X

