Delay Discounting	X		X	X
Actual Smoking Outcomes				
Timeline Follow-Back	X			X
Carbon Monoxide	X			X
Affect				
PANAS	X		X	X
Intervention Integrity/Acceptance				
Participant Adherence		X		
Therapist Adherence		X		

representing the mean z-score (using the BL mean and SD) on the two assessment measures (follow-up analyses will consider the two measures individually). Perceived Distress Tolerance will be assessed with the 10-Item Distress Intolerance Index (DII). Behavioral Distress Tolerance will be assessed with the computerized Mirror-Tracing Persistence Task (MTPT-C).

**Participant Adherence.** The number of sessions attended will be used to assess patient adherence.

**Interventionist Adherence.** All mindfulness sessions will be audiotaped. Independent master-level raters (available to [name]) will rate 10% of sessions for therapist adherence.

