3. To evaluate the impact of cognitive/affective target activation on proximal smoking risk/behavior following intervention, WM and DT will be added as time-varying predictors (TVPs) of outcome in MLM models for each of the 3 measures of smoking risk (susceptibility to smoking, implicit attitudes toward smoking, and delay discounting) and for actual smoking behavior (smoking behavior is dichotomous, so it will be analyzed using a GLMM with a logistic linking function). Because TVPs conflate the between-subjects and within-subjects components of the predictor, we will disaggregate each TVP into the participant's average level of the TVP across assessments, and their deviations from their average level, at each assessment. The regression coefficients for WM and DT predicting outcome in these models will indicate the degree to which each is related to smoking risk. The "deviations" component of the TVP will calculate the relation between both WM and DT with proximal measures of smoking risk within-subjects over time.

Power Analysis.

We used PinT 2.12 (Power in Two-Level Models)¹⁴⁸ to calculate the smallest effect size detectable with .80 power for each Aim. We assumed 150 total participants with 33% missing data (MLM and GLMM include all participants regardless of missing data, but the power is affected by number of obtained assessments per participant). We also assumed 6 covariates in each of the models. Alpha was set at .05. Aims 2 and 3: We have greater than .80 power to detect an effect size of $d = .29$ or larger for the MLM analyses. We have greater than .80 power to detect an effect size $\omega = .23$ or larger (between a small, $\omega = .10$, and a medium, $\omega = .30$ effect size) for the GLMM analysis (actual smoking behavior).

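### Aim 3 needs working memory and distress tolerance values at 1 month that are never scheduled, so the specified smoking model cannot estimate a post-intervention effect and the three proximal-risk models lose their 1-month rows

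*SAP*

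**What the plan says.** SAP, Data Analysis, item 3, states that "WM and DT will be added as time-varying predictors (TVPs) of outcome in MLM models for each of the 3 measures of smoking risk". It also applies them to actual smoking, a yes/no outcome analysed by a logistic mixed model (GLMM). Each predictor is separated into the participant's average over assessments and "their deviations from their average level, at each assessment". The deviation part "will calculate the relation between both WM and DT with proximal measures of smoking risk within-subjects over time". The SAP gives no lag, carry-forward or other rule for choosing the WM or DT value that goes with a 1-month outcome.

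Table 1 of the protocol sets the visits. The rows beginning "Working Memory (WM" and "Distress Tolerance (DT" are marked at baseline and 1 week after the intervention, and blank at 1 month. Susceptibility, the smoking implicit association test (IAT) and delay discounting are marked at all three visits. "Timeline Follow-Back" and carbon monoxide (CO) are marked at baseline and 1 month, and blank at 1 week. The Design Overview agrees: "Smoking behavior is assessed at one-month follow-up". The Smoking Status paragraph reads differently: "Self-reports of abstinence at each assessment visit will be verified by expired carbon monoxide".

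Under Power Analysis, the SAP reports .80 power for d = .29 (mixed models, Aims 2 and 3) and omega = .23 (the smoking GLMM).

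**The concern.** A time-varying predictor contributes only where it and the outcome are both available. If WM and DT stop at 1 week and smoking is next recorded at 1 month, the model meant to link the trained targets to later smoking has nothing to work with after baseline.

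Item 3 is the only planned analysis that ties WM and DT to smoking risk and behaviour. If the pairing is settled after the data are seen, there are several candidates: lag the 1-week value, carry it forward, or use the person average alone. These estimate different quantities, and the choice could follow the results. The stated power would also describe a model that cannot be run as specified.

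**Working it through.** **1. Schedule (Table 1).**

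| Variable | Baseline | 1 week | 1 month |
|---|---|---|---|
| WM, DT | yes | yes | no |
| Susceptibility, IAT, delay discounting | yes | yes | yes |
| Timeline follow-back, CO | yes | no | yes |

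**2. Rows with both predictor and outcome** (N = 150, no dropout, same-visit pairing).

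- Each proximal outcome: 150 × 3 = 450 scheduled and 150 × 2 = 300 usable. The 150 lost rows (one third) are all at 1 month.
- Smoking: 150 × 2 = 300 scheduled and 150 usable, all at baseline. There are 0 post-baseline rows and one row per person, so there is no within-person contrast.
- If the SAP's 33% missing is applied evenly: about 201 of 302 proximal rows, and about 100 of 201 smoking rows, still with none after baseline.

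**3. Smoking outcome in the usable rows.** The Design Overview describes 150 non-smoking adolescents. The Participants section says enrolment allows for possibly dropping current smokers from the final analyses. On that basis every usable row is expected to be a non-smoker. Any baseline smokers who were kept would still precede the intervention.

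**4. What the deviation contains.** With values x0 (baseline) and x1 (1 week), the average is (x0 + x1)/2 and the deviations are −(x1 − x0)/2 and +(x1 − x0)/2. The within-person term is therefore half the change score with opposite signs, and 0 for anyone measured once. This is usual for two occasions and is not an error in itself. It does mean that the proximal models reduce to a concurrent baseline-to-1-week change association.

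**5. Stated power.** A two-sided alpha is assumed, since sidedness is not given.

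- Omega: (1.9600 + 0.8416)/√N for a 1-df test. With N = 150, 2.8016/12.247 = 0.229, which matches .23. With 150 × 0.67 = 100.5, it is 0.279. So .23 fits a full-sample test, not the usable rows found in step 2.
- d = .29 cannot be firmly reproduced, because PinT needs variance components and a number of assessments that the SAP does not report. The nearest simple match is one coefficient on about 100 people: 2.8016/√100 = 0.280, or 0.289 with N = 94.
- If .29 assumed three usable assessments (an assumption), keeping two gives .29 × √(3/2) = 0.36 by total rows, or .29 × √2 = 0.41 by within-person information.

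**6. What a lagged model would have.** With 1-week WM and DT paired to 1-month smoking, there are up to 150 rows, or about 100 at 67%, one per person. The documents give no 1-month smoking rate. At assumed rates of 1% to 10%, events would number 1.5 to 15 of 150, or about 1 to 10 of 100. The model has 4 WM/DT terms (two at each visit), 2 arm terms and 5 covariate terms (3 dummies for four parental-smoking categories, plus peer smoking and sensation seeking). That makes 11 coefficients, hence the case for penalisation.

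**The case against.** A reader might infer that no WM- or DT-to-smoking estimate is possible, that all follow-up data are lost, or that Aim 2 fails too. The documents do not support that.

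- **Person average.** It does not vary over time and could be attached to 1-month smoking. The SAP sentence on what the deviation part estimates names proximal risk, not smoking. This stands. But a model with the average alone is not the one specified, and the average mixes pre- and post-intervention values, so it blurs the effect of changing the target.
- **Lagged reading.** Table 1 calls WM and DT mediators, and item 3 concerns outcomes after the intervention, so a lag may be intended. The wording allows this but does not state it.
- **Smoking status at 1 week.** The CO sentence could mean a 1-week check, and timeline follow-back can date onset. Either would add 1-week pairs. Table 1 and the Design Overview point the other way, and no reconstruction of 1-week status is planned.
- **Constant baseline.** This is expected rather than established. The protocol treats dropping current smokers as a possibility, and the dichotomous outcome is not defined.
- **What survives.** The proximal models keep the 1-week visit. Arm contrasts that omit WM and DT are untouched, including those at 1 month. Aim 2 contrasts on WM and DT stand at 1 week; centering at follow-up simply does not apply to them.
- **Benchmarks.** The go/no-go criterion rests on intervention effects, not on the WM or DT coefficient for smoking.

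The SAP's remark that mixed models include participants regardless of missing data does not answer the point. It does not supply a predictor that is never scheduled at a visit, and imputation would have no observed 1-month WM or DT to learn from.

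**Conclusion.** The concern holds for the Aim 3 models as written, assuming same-visit pairing and the Table 1 schedule. The smoking GLMM has 150 of 300 scheduled rows with a deviation value, all before the intervention, where smoking is expected to be constant. It cannot estimate a WM or DT effect on smoking after the intervention. Each proximal model loses 150 of 450 scheduled rows, exactly the 1-month visit, before any dropout. The defect lies in the specified pairing and not in the data collected, because Table 1 already contains what a lagged analysis needs. The quoted power of d = .29 and omega = .23 should not be carried over to the models that can be fitted.

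**What to change.** For 1-month outcomes, replace the concurrent model with a lagged one: regress the outcome on 1-week WM and DT, adjusted for baseline WM and DT, arm and the planned covariates. Add the baseline outcome for susceptibility, IAT and delay discounting only. For smoking, fit a single-occasion penalised logistic model of 1-month status with no baseline-smoking term, since that variable is expected to be constant. Define the dichotomous outcome, including whether smoking that began before the 1-week visit counts.

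Keep the baseline/1-week concurrent model as a secondary association analysis. State that WM and DT contrasts under Aim 2 are made at 1 week only. Restate the Aim 3 power figures for the models actually fitted, and reconcile the CO sentence under Smoking Status with Table 1.

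The cost is a SAP revision, a new power calculation and a little more analysis work. The stated power will probably look less favourable, and the smoking estimate will be imprecise if events are few. The lagged model gives temporal order, but its WM and DT coefficients remain observational. No new data are needed.

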**Participants.** We propose to study 150 adolescents (expected mean age = 13) enrolled in high school as a freshman or sophomore. Reflecting the demographics of the community in which we are recruiting, we expect approximately 70% of the sample to be at or below the poverty level, balanced between males and females, with the majority from an ethnic minority background. [name] previous work among adolescents suggests that at this age, smoking rates are very low. Among a sample of 185 adolescents, only 3.8% reported smoking regularly and 87% reported having smoked once ever, or never at all. In sum, we do not believe that smoking status at this age is a problem, however, our targeted enrollment (N = 150) has accounted for the possibility of having to drop current smokers in the final analyses as well as attrition.

**Feasibility.** [name] has experience working with low-income youth, and we plan to engage the following recommended best practices to ensure sufficient recruitment and retention. We attach letters of support from local high schools and community centers who serve individuals with characteristics suitable to our study. The headmasters of two local high schools have demonstrated enthusiasm for our study and plan to provide both institutional and social support in our endeavor. Additionally, we have budgeted for financial compensation for all components of the study (assessments and interventions), as well as snacks for the intervention sessions in order to improve enrollment and retention. The following projects and published studies demonstrate the productivity and preparedness of our research team for investigations in the impact of WM and mindfulness training on risk factors and smoking-related outcomes in at-risk youth. [name] is a developmental psychologist and expert in the acquisition and longitudinal study of low-income youth. Her work focuses on documentation of the effects of stress in this population. She has examined the impact of poverty on

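### The SAP's d = .29 at 80% power is not supported for the Aim 2 pairwise arm contrasts; with ordinary assumptions they detect about d = .40 to .70

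*SAP*

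**What the plan says.** The Power Analysis section of the SAP used PinT to "calculate the smallest effect size detectable with .80 power for each Aim". Its inputs are: "We assumed 150 total participants with 33% missing data", six covariates, and "Alpha was set at .05". Missingness is treated as lost assessments rather than lost participants, because "the power is affected by number of obtained assessments per participant". The result is one figure, given for Aims 2 and 3 together: "We have greater than .80 power to detect an effect size of $d = .29$ or larger for the MLM analyses".

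The section does not state the sidedness of the test, the intraclass correlation (ICC) or baseline-to-post correlation, the variance explained by covariates, the standard deviation that defines d, or the coefficient the figure refers to.

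The two aims test different things. Under the SAP's Data Analysis heading, the opening paragraph and item 2 set Aim 2 up as dummy-variable contrasts of each active arm with control, then of the two active arms, at a chosen visit. Item 3 tests WM and DT as time-varying predictors of smoking risk across the whole sample. The protocol's Design Overview describes "block randomization of 150 non-smoking adolescents to one of three intervention conditions". Its assessment table (Table 1) schedules WM and DT at baseline and one week after intervention only.

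**The concern.** An effect of .29 is small for a comparison of two arms of about 50, and smaller still relative to what such arms can detect with a third of the data missing. The six covariates and the baseline measurement can narrow the gap, but the SAP does not say by how much.

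The figure matters when a null result is interpreted. The protocol's Benchmarks section makes significant intervention effects on delay discounting and distress tolerance a go/no-go criterion. The DT arm contrast in item 2 feeds that decision. A reader who trusts the power paragraph could take a non-significant DT contrast as evidence against an effect of .29, and drop a target that the trial had little chance of confirming.

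**Working it through.** **Inputs.** From the SAP: N = 150, 33% missing, alpha .05, power .80, stated d = .29. From the protocol: three arms. Assumed, because not stated: equal allocation (150/3 = 50 per arm), two-sided testing, and the correlations and R² shown below. If a third of post-intervention values are missing, 50 × .67 = 33.5 per arm are observed.

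**1. Trying to reproduce .29.** For two arms of n, the minimum detectable effect (MDE) is (1.960 + 0.842) × √(2/n) = 2.80 × √(2/n).

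- n = 50: 2.80 × √.04 = .56 (noncentral t: .566)
- n = 33.5: 2.80 × √.0597 = .68 (noncentral t: .695)
- n needed for .29: 2 × (2.8016/.29)² = 186.7, or 187 per arm

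One-sided testing gives 2.486 × √.04 = .50 at 50 per arm and .61 at 33.5. Pooling both active arms against control gives 2.80 × √(1/100 + 1/50) = .49. None of these reaches .29.

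**2. Adding baseline adjustment.** Multiply the MDE by √(1 − r²), where r is the baseline-to-post correlation (noncentral t, two-sided .05):

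| r (assumed) | MDE, 50 per arm | Power at .29 | MDE, 33.5 per arm | Power at .29 |
|---|---|---|---|---|
| none | .57 | 30% | .70 | 21% |
| .5 | .49 | 38% | .60 | 27% |
| .6 | .45 | 43% | .56 | 31% |
| .7 | .40 | 52% | .50 | 37% |
| .8 | .34 | 67% | .42 | 50% |

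For .29 by this route alone, r = √(1 − (.29/.566)²) = .86 with complete data, or √(1 − (.29/.695)²) = .91 with 33% missing.

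**3. The group-by-time model as the SAP describes it.** The SAP does not list the baseline outcome as a covariate, so I also used a two-visit repeated-measures model with the contrast read at the post-intervention visit, baseline means left free and 33% missing (normal approximation). For ICC from .3 to .9 the MDE is .59 to .68 and power at .29 is 22% to 28%. If the covariates explain 20% to 40% of the variance, the MDE is .45 to .61 and power 27% to 43%.

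**4. Where a value near .29 does appear.** For one standardised coefficient estimated on the whole sample, the MDE is 2.80/√N: .280 at N = 100 and .289 at N = 94. That is the type of test in Aim 3. The companion figure for smoking behaviour, ω = .23, matches 2.80/√150 = .229, with no deduction for missing data. No single recipe therefore explains both figures, and the origin of .29 remains an inference.

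**The case against.** The strongest reply is that the SAP's inputs are incomplete, so its figure cannot be shown to be false. That stands. Strong assumptions would deliver .29: at 50 per arm, r = .8 with covariates explaining a further 27% of the residual variance gives .566 × √(1 − .64) × √(1 − .27) = .566 × .600 × .854 = .29. The documents give no such values, so the figure is unsupported for arm contrasts rather than disproved.

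The second reply is that 33.5 per arm treats missing assessments as missing people, whereas the model keeps everyone. That is fair, and 33.5 is the pessimistic end. The concession is small here, because WM and DT have one post-intervention value each. A participant who lacks it informs the contrast only through baseline, and step 3 shows how little that recovers when the baseline means are left free.

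The third reply is that the sentence also covers Aim 3. It does, and for a whole-sample coefficient about .28 to .29 is plausible.

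Three stronger readings are tempting and should be resisted:

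- A reader might infer that the trial's true power at .29 is 21% to 30%. Those values assume no gain from covariates or baseline.
- A reader might infer that .29 was computed on 94 people (150 × .67, less six covariates). The SAP does not say so, and N = 100 fits as well.
- A reader might infer that every Aim 2 contrast is a go/no-go test. The Benchmarks section names delay discounting and DT, while item 2 of the SAP contrasts WM and DT; only DT is in both.

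**Conclusion.** The point holds for the Aim 2 pairwise contrasts and not for the sentence as a whole. One effect size is attached to two different tests, and the stated inputs do not lead to it for the arm contrasts.

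With equal allocation and two-sided .05, the detectable effect is about .57 to .70 unadjusted, and about .40 to .60 with a baseline correlation of .5 to .7, depending on missingness. Power at .29 over all those cases runs from about 21% to 52%. Only a correlation near .86 to .91, or a somewhat lower one combined with substantial covariate R², would make the claim true. The SAP states neither.

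**What to change.** Revise the Power Analysis paragraph of the SAP as follows:

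- Name the coefficient that d = .29 refers to and the standard deviation that defines d. If it is the Aim 3 whole-sample coefficient, restrict the figure to that.
- Give the Aim 2 detectable effect per pairwise contrast as a conditional range: about .57 (complete) to .70 (33% of post-intervention values missing) unadjusted; about .40 to .49 and .50 to .60 respectively with baseline adjustment at correlations of .5 to .7.
- State the assumed correlation or ICC, covariate R², missingness, allocation and sidedness beside those figures.
- Commit to reporting the DT arm contrast that feeds the Benchmarks decision as an estimate with a confidence interval, so that a non-significant result is not read as excluding .29.

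The cost is a rewritten paragraph and a less favourable stated detectable effect. Sample size and model do not change.
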